### **Aims**

The proposed work is divided into two parts through an observational and an interventional study.

1. Observational study: characterise individuals with severe hypoglycemia.
2. Interventional preliminary study: investigate the effect of regular glucose monitoring and specialist nurse input into a) future hypoglycemic events, b) confidence with diabetes management/quality of life and c) clinical outcome.

[figure not shown]

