### Observational study

Various details will be collected to elucidate the characteristics of patients undergoing severe hypoglycemia requiring emergency services intervention.

**Demographic and general data.** Address, age, sex, type of diabetes and duration, weight, body mass index, blood pressure, presence of macrovascular and microvascular complications, current treatment, status at home (living alone), driving status, alcohol consumption, smoking history, mobility, non-diabetes related co-morbidities. We will also clarify who made the ambulance call (patient/carer/other).

**Patient questionnaire (see appendix 1).** This will address whether a patient feels confident regarding managing his/her diabetes, how often glucose is monitored, can the patient adjust insulin, does the patient understand the dangers of hypoglycemia, presence of hypoglycemia awareness, frequency of low glucose levels, treatment options of hypoglycemia.

**Examination.** Check injection sites for lipoatrophy or lipohypertrophy and examine for signs of peripheral neuropathy (monofilament test).

**Blood and urine tests.** These will be arranged as part of routine clinical care in both groups, unless recent blood tests have been done. The following tests will be included: HbA1c, urea and electrolytes, liver function tests, full lipid profile, thyroid function tests (where appropriate), urinary albumin/creatinine ratio (ACR). HbA1c will be measured every 3 months, U&Es, LFTs and lipid profile 6 monthly. ACR will be checked at enrolment and at 12 months. All above tests will be requested more frequently if clinically indicated.

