as dietitian support may be sought if the research nurse and/or PI find this to be necessary. In cases of newly diagnosed (or suspected) clinical conditions, referrals to an appropriate specialty will be made after review by the PI. If social circumstances are found to be inappropriate, for example in the case of older individuals not managing on their own, the physician in charge of the patient will be informed and steps will be taken to provide support according to the need of each individual.

In summary, the research nurse will concentrate on establishing the cause of the severe hypoglycemic episode and together with the PI will alter treatment, involve other diabetes/non-diabetes disciplines as appropriate and introduce changes to social support as required.

The research nurse will contact the patient weekly for the first month, every two weeks for the following month followed by contact at months 3, 6 and 12. Face to face contact with the patient will be arranged at enrolment, 1, 3 and 12 months. Patient will be asked to fill in the questionnaire at enrolment and end of 3rd month, with selected patients asked to complete the form again at 12 months (explained in Figure 4). Blood tests will be arranged as detailed above. In the standard arm, patient will be contacted only once as per current arrangement and subsequent treatment left to the discretion of the attending physician (summarised in Figure 4).

**Figure 4.** Summary of the preliminary interventional part of the study. U&Es: urea and electrolytes, LFTs: liver function tests, UACR: urinary albumin/creatinine ratio, MACE: major adverse cardiovascular events, m:

month, d: day. Questionnaire will be done at enrolment and 3 months in both groups. If a significant difference exists between the two time points in the same patient, the questionnaire will be repeated at 12 months. Clinical outcome at 12 months will also include frequency of hypoglycemia, analysed separately.

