### **Statistical analysis**

The observational part of the study will collect various data and will be the basis for future studies. Power calculations were based on the interventional study. Given our current data showing a death rate in excess of 17% within one year of hypoglycemia, we calculated that 200 individuals are needed in each of the study arms to detect a drop in mortality to 10% in intensively monitored patients (at  $p=0.05$ ). Between group analysis will be done using unpaired  $t$ -test for normally distributed data and the non-parametric Mann-Whitney test will be used for data that are not normally distributed. For categorical data, 2X2 contingency tables will be used and multiple regression analysis will be performed to determine potential causes of hypoglycemia.

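### The planned between-arm tests are valid but ignore the enrolment values already collected, and the plan does not say whether follow-up values or changes are compared

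*Combined protocol and SAP*

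**What the plan says.** The Statistical analysis section gives three between-group methods: the unpaired t-test for normally distributed data, 2X2 tables for categorical data, and, for the rest, "the non-parametric Mann-Whitney test will be used for data that are not normally distributed". Its one regression model is for finding causes of hypoglycemia, not for comparing arms.

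Enrolment values are nevertheless planned:

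- **Questionnaire.** The second part of the interventional aim is "b) confidence with diabetes management/quality of life and c) clinical outcome". The Figure 4 legend says "Questionnaire will be done at enrolment and 3 months in both groups", and then "If a significant difference exists between the two time points in the same patient, the questionnaire will be repeated at 12 months". The text above that legend says "In the standard arm, patient will be contacted only once as per current arrangement".
- **Laboratory values.** The Observational study section says of blood and urine tests: "These will be arranged as part of routine clinical care in both groups, unless recent blood tests have been done". It adds "HbA1c will be measured every 3 months", and schedules ACR at enrolment and at 12 months.

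No section describes a comparison adjusted for enrolment values, or says whether the named tests apply to follow-up values or to changes from enrolment.

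**The concern.** When an outcome is measured before and after randomisation, part of its spread at follow-up is already explained by the first measurement. A test on follow-up values leaves that part in the error term. A test on change uses the enrolment value but subtracts all of it, which adds noise when the two measurements are only weakly related.

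The plan leaves open which of the two it means, and they can differ widely in power. The choice could therefore be made after the data are seen. The aim most exposed is confidence and quality of life, which rests on the questionnaire. HbA1c and ACR are affected in the same way, but the plan does not tie them to an aim.

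**Working it through.** **The plan's own figure.** The only sample-size figure is 200 per arm for a fall in mortality from 17% to 10% at p=0.05. Power is not stated, so it cannot be reproduced from its own inputs; 200 per arm gives 53.5% power two-sided. That is a separate matter, because mortality has no enrolment value. The plan gives no figure for the questionnaire or laboratory outcomes.

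**Inputs from the plan.** 200 per arm, with 12-month mortality of 17.1% (Background) and 10% (Statistical analysis). Survivors: 200 × (1 − 0.171) = 166 and 200 × 0.90 = 180.

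**Assumptions.** Effect 0.25 SD, two-sided 5% level, equal SD at both times, correlation r = 0.2, 0.3, 0.5 or 0.7.

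**Step 1: variance per patient, in units of SD².**

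- Follow-up value: 1
- Change: 2(1 − r)
- ANCOVA: 1 − r²

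ANCOVA is never the largest: 1 − r² ≤ 1, and 2(1 − r) − (1 − r²) = (1 − r)² ≥ 0. This is a large-sample result.

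**Step 2: power.** The standard error factor is √(1/166 + 1/180) = 0.1076. On follow-up values the noncentrality is 0.25/0.1076 = 2.32. For the other two analyses, divide 2.32 by the square root of the variance in step 1. The noncentral t distribution gives:

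| r | Follow-up t-test | t-test on change | ANCOVA |
|---|---|---|---|
| 0.2 | 64% | 45% | 66% |
| 0.3 | 64% | 50% | 68% |
| 0.5 | 64% | 64% | 76% |
| 0.7 | 64% | 85% | 90% |

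**Step 3: the same in patients.** To match ANCOVA at r = 0.2, 0.3, 0.5 and 0.7:

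- a follow-up comparison needs 1/(1 − r²) − 1 = 4, 10, 33 and 96% more patients;
- a change comparison needs 2/(1 + r) − 1 = 67, 54, 33 and 18% more.

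The two losses run in opposite directions as r rises.

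**Step 4: five-level questionnaire item, by simulation.** 2000 trials per setting, 180 responders per arm, latent shift 0.25 SD, cumulative response proportions 20, 45, 70 and 90%. Simulation error is about √(0.6 × 0.4/2000), or 1 point.

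| r | Mann-Whitney, 3-month response | Mann-Whitney, change | Proportional odds with enrolment response |
|---|---|---|---|
| 0.2 | 61% | 40% | 63% |
| 0.3 | 61% | 45% | 65% |
| 0.5 | 60% | 56% | 71% |
| 0.7 | 60% | 73% | 83% |

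Over two response distributions and 140 or 180 responders per arm, the gain over the 3-month Mann-Whitney test was 1–2, 3, 8–11 and 20–23 points. A linear model on the 1–5 score was within 1 point of proportional odds in the setting tabulated, the only one in which it was run. The proportional-odds test had a null rejection rate of 5.0–5.8%.

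**Step 5: validity of the named tests.** Simulating 4000 trials per setting with 200 per arm and no effect, the t-test rejected in 4.9–5.2% and Mann-Whitney in 4.8–5.2%, for r from 0 to 0.7.

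**The case against.** The strongest reply is that this is a preference. The tests are valid, the study is described as preliminary, no power is claimed for these outcomes, and at r = 0.2–0.3 the gain over follow-up values is only a few points. It stands that this is lost efficiency rather than error, and that its size cannot be fixed from the documents. It does not remove the point: adjustment is at least as efficient in large samples as either reading of the plan, and it uses data already planned.

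A second objection is that adjusting all 15 Appendix 1 items would create its own problem. That is right. Fifteen independent tests at 5% give 1 − 0.95^15 = 54% chance of at least one false positive. One item applies to insulin users only. Another looks back 12 months, so at 3 months about nine of those months precede enrolment. The items serving the aim must be named.

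Three stronger readings are tempting and not supported:

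- **Chance imbalance at enrolment biases the planned tests.** Under randomisation it is already in their standard error, as step 5 confirms.
- **The loss always grows with correlation.** That holds only if follow-up values are compared. Against change, the loss shrinks as correlation rises.
- **Longer survival in the intensive arm distorts the comparison of hypoglycemia frequency.** The Figure 4 legend says only "Clinical outcome at 12 months will also include frequency of hypoglycemia, analysed separately". The scale is not stated, and the documents do not give an event rate per patient-year, so no such claim is made here.

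**Conclusion.** The point holds as a moderate, inexpensive improvement and not as a fault in validity. The named tests make no use of enrolment values, and the plan leaves follow-up or change unspecified. For a 0.25 SD effect among 166 and 180 survivors, ANCOVA gains about 2 to 26 points over follow-up values as r goes from 0.2 to 0.7, and about 21 down to 5 points over change. The questionnaire simulation shows the same pattern. These sizes rest on assumed correlations, effect and responder numbers.

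The mortality comparison is untouched. Twelve-month values exist only for survivors under any of these analyses.

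**What to change.** Add to the Statistical analysis section:

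> The questionnaire items on confidence and quality of life (Appendix 1, named before any analysis by arm) will be compared between arms at 3 months by regression (proportional-odds, or linear on the 1–5 score) on arm and enrolment response. The remaining items are exploratory: the insulin-adjustment item is analysed in insulin users only, and the item with a 12-month look-back is not compared at 3 months. HbA1c (as measured) and ACR (log scale) at 12 months will be compared by ANCOVA on arm and the latest value on or before randomisation; a missing enrolment value is set to the mean over both arms. The t-test or Mann-Whitney test on follow-up values is a sensitivity analysis. The selective 12-month questionnaire repeat is descriptive only.

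State which of the two questionnaire models is used before data are seen. Taking the latest value on or before randomisation covers accepted recent routine results.

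The repeat is descriptive because patients are selected for it on their own change in response.

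Reconcile the two statements in the Interventional study section: a single contact in the standard arm, and a 3-month questionnaire in both groups. Any 3-month comparison, adjusted or not, depends on this.

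The cost is analysis wording only, provided that questionnaire is obtained in both arms. The downside is modest reliance on a model.

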**Appendix 1 (patient questionnaire-will not be seen by the research nurse)**

**How much do you feel you understand about diabetes?**

1. More than enough
2. Just enough
3. Could do with more knowledge
4. I know very little
5. I do not understand diabetes at all

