**For insulin users: Do you know how to adjust/modify your insulin doses according to your glucose readings?**

1. I am in full control.
2. Yes, but I may need occasional advice.
3. Yes, but prefer to have advice for reassurance.
4. I have little knowledge.
5. I have no idea.

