**Are you aware of the guidance regarding hypoglycemia and driving?**

1. Yes, I am fully aware of the guidelines.
2. I probably know all the details
3. I know some of the details but not all
4. I know very little.
5. I have no idea.

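### The plan's categorical-data rule does not suit 15 ordered five-level questionnaire items: it risks an unstated cut, leaves multiplicity open and ignores the enrolment answers

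*Combined protocol and SAP*

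**What the plan says.** The Aims section gives the interventional study three targets, the second being "confidence with diabetes management/quality of life". The instrument for it is Appendix 1, headed "patient questionnaire-will not be seen by the research nurse". It runs from "How much do you feel you understand about diabetes" to "Are you aware of the guidance regarding hypoglycemia and driving": 15 items, each with answers numbered 1 (most favourable) to 5 (least favourable). One item is limited to a subgroup: "For insulin users: Do you know how to adjust/modify your insulin doses according to your glucose readings".

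The Interventional study section has both arms complete the form at enrolment and at 3 months. The Figure 4 caption adds: "If a significant difference exists between the two time points in the same patient, the questionnaire will be repeated at 12 months".

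The Statistical analysis section is one paragraph. It gives an unpaired t-test for normal data, Mann-Whitney for non-normal data, and then, for categorical data, "2X2 contingency tables will be used and multiple regression analysis will be performed". The multiple regression is reserved for finding causes of hypoglycemia. The questionnaire is not mentioned there. The readable text gives no total or domain score, key item, cut-point or multiplicity rule.

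**The concern.** A five-level answer fits a 2x2 table only after it has been cut in two. The plan states no cut, so the cut could be chosen once the data are known. Cutting also throws away the ordering within each half.

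With no summary score, there may be as many between-arm comparisons as there are items. Aim 2(b) would then have many chances of a false positive and no single answer.

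The listed two-group tests also compare the arms at one time point only. Each patient's enrolment answer is collected in both arms but would play no part in the 3-month comparison.

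**Working it through.** The plan gives no figure for the questionnaire, so there is none to reproduce. Its 200 per arm comes from the mortality calculation and is used below only as the arm size.

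**Inputs from the documents:** 15 items (14 for patients not on insulin); five ordered answers each; 200 per arm; significance level 0.05, taken as two-sided because sidedness is not stated.

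**Assumptions, because the documents give no response data:** proportional odds; equal fifths or a skewed 40/30/15/10/5 split of answers; a common odds ratio of 1.65; between-item correlations of 0.3, 0.5 and 0.7.

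**1. Information lost by cutting.** For a small shift under proportional odds, information is proportional to 1 − Σp³, where p are the category proportions.

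- Equal fifths, all levels: 1 − 5 × 0.2³ = 0.96.
- Skewed split, all levels: 1 − (0.064 + 0.027 + 0.003375 + 0.001 + 0.000125) = 0.9045.
- Cut at 40/60: 1 − (0.064 + 0.216) = 0.72.
- Cut at 80/20: 1 − (0.512 + 0.008) = 0.48.
- Cut at 85/15: 1 − (0.614125 + 0.003375) = 0.3825.

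| Answers | Cut | Relative efficiency |
|---|---|---|
| Equal fifths | 40/60 (best) | 0.72 / 0.96 = 0.75 |
| Skewed | 40/60 (best) | 0.72 / 0.9045 = 0.80 |
| Equal fifths | 80/20 | 0.48 / 0.96 = 0.50 |
| Skewed | 85/15 | 0.3825 / 0.9045 = 0.42 |

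An efficiency of 0.75 makes 200 per arm worth 0.75 × 200 = 150 per arm; at 0.42 it is worth 84.

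**2. The same loss as power.** This was simulated with 200 per arm, odds ratio 1.65 and 6,000 trials per setting. With equal fifths, Mann-Whitney on five levels has power of about 0.80, against 0.46 to 0.70 for a 2x2 table, depending on the cut. For the skewed split and a symmetric 10/20/40/20/10 split, Mann-Whitney has 0.78 to 0.79 and the 2x2 table 0.16 to 0.71.

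**3. False positives if items are tested singly.** For k independent tests at 0.05, the chance of at least one false positive is 1 − 0.95^k.

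- k = 15: 1 − 0.95^15 = 0.537.
- k = 14: 1 − 0.95^14 = 0.512.

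Items on one form will be correlated, so this was simulated with 200 per arm, equal fifths and 3,000 trials:

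| Assumed item correlation | Mann-Whitney, 15 items | Fixed 2x2 cut, 15 items |
|---|---|---|
| 0.3 | 0.48 | 0.48 |
| 0.5 | 0.40 | 0.44 |
| 0.7 | 0.29 | 0.36 |

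A Bonferroni limit for 15 items would be 0.05 / 15 = 0.0033. One pre-specified score needs one test at 0.05.

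**4. Enrolment answers.** If the enrolment and 3-month scores correlate at r, adjusting for the enrolment score multiplies the variance of the arm comparison by about 1 − r². The documents give no r, so no size is claimed. The direction is certain for any r other than zero.

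**The case against.** The strongest reply is that the Mann-Whitney rule is not restricted to continuous measurements. Answers coded 1 to 5 are ordered and non-normal, so the plan already allows an analysis on all five levels, and the 2x2 sentence may be meant only for outcomes such as death. This stands in part. A reader might infer that the answers must be dichotomised, and the documents do not support that. They leave the choice of method open.

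Three further inferences also go too far:

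- **That items will be tested one by one.** This is stated nowhere. It follows only from the absence of a score, so the figures in step 3 are conditional. The 12-month repeat rule could even suggest an intended per-patient summary. The image of Figure 4 is not available, so the definition of that rule cannot be judged fully.
- **That dichotomising inflates false positives.** The inflation comes from the number of unadjusted tests. Mann-Whitney on 15 items inflates in a similar way. Only a cut chosen after seeing the data would add to it, and the documents do not say that this will happen.
- **That at least a quarter of the information is lost.** The skewed example loses a fifth at its best cut.

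It is also fair to say that the interventional study is called preliminary, is sized on mortality, and makes no confirmatory claim for the questionnaire. That limits the seriousness of the point but does not supply a method for a stated aim.

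**Conclusion.** The point holds in a limited form. The questionnaire behind aim 2(b) has 15 ordered five-level items. The only rule worded for categorical data is a 2x2 table, and the plan does not say whether that rule or Mann-Whitney applies. Neither uses the enrolment answers.

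Under the literal reading, about a fifth or more of the information is lost, and half or more with a poor cut. These sizes rest on assumed response distributions and proportional odds. The false-positive risk applies only if items are tested singly and unadjusted: 54% is the value under independence, and roughly 29% to 48% is more realistic over the assumed correlations.

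This should be changed, but it does not touch the mortality comparison on which the trial is sized.

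**What to change.** In the Statistical analysis section:

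- Restrict 2x2 tables to outcomes that are truly binary.
- Analyse single questionnaire items on all five levels, by a proportional-odds model or Mann-Whitney, and label them descriptive.
- Pre-specify one confidence and quality-of-life score for aim 2(b), built from items that match the aim and apply to every patient.
- Compare the arms on that score at 3 months in a model that adjusts for the enrolment score.

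Adding up every item that applies to all patients is tempting because all run in the same direction, but it would mix aims. Leave out:

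- the insulin-only item;
- the two items on nurse support;
- the two items on how often hypoglycemia occurs. These are closer to aim 2(a), and the Figure 4 caption has hypoglycemia frequency analysed separately. The item on assisted attacks also looks back 12 months, so at month 3 about 9 of those months precede enrolment.

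This leaves at most 15 − 1 − 2 − 2 = 10 candidates. The investigators should confirm whether two of them belong. The glucose-testing item has as its best answer the behaviour encouraged in the intensive arm, and the item on local education rates a service. Without both, 8 remain. The same score would give the 12-month repeat rule a per-patient measure of change.

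The cost is a short paragraph and no new data. The downside is that single items can no longer be claimed as significant findings, and the score weights its items equally although they may differ in importance.

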**Appendix 1 (patient questionnaire-will not be seen by the research nurse)**

**How much do you feel you understand about diabetes?**

1. More than enough
2. Just enough
3. Could do with more knowledge
4. I know very little
5. I do not understand diabetes at all

**Do you think diabetes education in your area is adequate at present?**

1. Perfect
2. Acceptable
3. Could be better
4. Poor
5. Non-existent

**How often do you test your blood glucose (sugar) levels?**

1. At least twice a day with additional testing as needed.
2. At least once a day.
3. Less than once a day but at least twice a week.
4. Less than once a week.
5. Never.

**Do you get concerned about testing your blood glucose and what it may show?**

1. Never as I know what to do.
2. I do get concerned sometimes but this is rare.
3. I often get concerned.
4. I am always concerned.
5. I am terrified of checking my glucose levels as I have no idea how to manage the various numbers.

**Do you check your blood glucose when you feel hypoglycemic?**

1. Always.
2. Almost always.
3. Sometimes
4. Rarely.
5. Never.

